1.2. Trial Design

This is a Phase 2 multicenter, double-blind, placebo-controlled, randomized study to evaluate the antiviral activity, clinical outcomes, safety, tolerability, and PK/PD relationships of different oral dose levels of JNJ-53718678 in children ≥ 28 days and ≤ 3 years of age with RSV disease (hospitalized subjects [Cohort 1] or outpatients [Cohort 2]).

Up to 4 IAs are planned for this study. For the full trial design please refer to Section 3.1 of the protocol.

The total number of subjects is planned to be approximately 294 (approximately 144 in Cohort 1 and approximately 150 in Cohort 2; approximately 196 subjects receiving JNJ-53718678 and approximately 98 subjects receiving placebo). The sample size of Cohort 2 may be re-estimated to a maximum of 300 in Cohort 2 based upon results from the third IA.

Overall, for both cohorts, the study will include a Screening Period (Day -1 to Day 1), a Treatment Period (Day 1 to Day 8), and a Follow-up Period (Day 9 to Day 28 [± 3]). The total study duration for each subject will be approximately 29 days (Screening included). A diagram of the study design is provided in [Figure 1](#).

Figure 1: Schematic Overview of the Design of Study 53718678RSV2002

a) Cohort 1 after discharge and Cohort 2.

b) Subjects can be discharged as of Day 2.

c) A subcohort of 6 subjects >2 and ≤3 years included in Cohort 1 will be included ([low dose JNJ-53718678 [N=2], high dose JNJ-53718678 [N=2], and placebo [N=2]]). While this subcohort is ongoing, additional subjects >2 and ≤3 years of age are not allowed to be enrolled in the Cohort 2.

d) In case of ongoing AE(s).

e) The study will start with Cohort 1 (including the subcohort). After the first interim analysis an IDMC will review the interim data, and will issue its recommendation to the sponsor, based on which the Sponsor Committee will decide whether to initiate enrollment in Cohort 2, while hospitalized subjects continue to be enrolled.

f) Sample size of Cohort 2 might be re-estimated to a maximum of N=300.

Note: Age group 1: ≥28 days and <3 months of age; Age group 2: ≥3 months and <6 months; Age group 3: ≥6 months and ≤3 years

In Cohort 1, a subcohort of 6 subjects >2 and ≤3 years will be included, who will follow in general the same assessment schedule as for all subjects enrolled in Cohort 1, although with a specific PK sampling schedule, assigned at randomization. Of note, if the subcohort is fully enrolled, additional subjects >2 and ≤3 years of age can be enrolled in Cohort 1 and will follow all Cohort 1 procedures. Within each cohort, except for the subcohort, randomization will be stratified by time of symptom onset (≤3 days vs >3 days to ≤5 days before randomization) and by presence of risk factors for severe RSV disease (otherwise healthy vs presence of [a] risk factor[s] for severe RSV disease). Subjects with symptom onset ≤3 days before randomization must account for a minimum of 45 % of all enrolled subjects in Cohorts 1 and 2 (i.e. maximum 55% of subjects can be enrolled in the >3 days stratum). To guarantee balance between strata for the IA, enrollment in the >3 days since symptoms onset stratum might be temporarily paused prior to an interim analysis and stopped prior to the final analysis. More details regarding randomization can be found in Section 1.5.

For dosing purposes, 3 age groups are defined depending on the subject's age at the time of consent:

- Age group 1: ≥28 days and <3 months of age (28 to 91 days of age, extremes included, for IWRS purposes)
- Age group 2: ≥3 months and <6 months of age (92 to 182 days of age, extremes included, for IWRS purposes)
- Age group 3: ≥6 months and ≤3 years of age (183 to 1,096 days, extremes included, for IWRS purposes)

Prior to Amendment #4 (dated 26 May 2020): study drug to be administered once daily (*quaque die* [QD]) for a planned treatment duration of 7 days. Doses are based on bodyweight and age group, but are identical for both cohorts:

- High Dose (Cohort 1: n = 48 [target]; Cohort 2: n = 50 [target]):
 - Age group 1: 5 mg JNJ-53718678/kg bodyweight
 - Age group 2: 6 mg JNJ-53718678/kg bodyweight
 - Age group 3: 9 mg JNJ-53718678/kg bodyweight
- Low Dose (Cohort 1: n = 48 [target]; Cohort 2: n = 50 [target]):
 - Age group 1: 1.7 mg JNJ-53718678/kg bodyweight
 - Age group 2: 2 mg JNJ-53718678/kg bodyweight
 - Age group 3: 3 mg JNJ-53718678/kg bodyweight
- Placebo (Cohort 1: n = 48 [target]; Cohort 2: n = 50 [target]): those randomized to a placebo regimen will subsequently be randomized 1:1 to receive either:
 - High volume placebo:
 - Age groups 1, 2, and 3: matching placebo (volume of placebo suspension to match the calculated volume of the JNJ-53718678 suspension for the high dose)
 - Low volume placebo:
 - Age groups 1, 2, and 3: matching placebo (volume of placebo suspension to match the calculated volume of the JNJ-53718678 suspension for the low dose)

Post-amendment #4 (dated 26 May 2020): Cohort 1 enrollment complete with all randomized and treated subjects receiving once daily dosing for a planned treatment duration of 7 days. Cohort 2 enrollment continuing with study drug to be administered twice daily (*bis in die* [BID]) for a planned treatment duration of 7 days. Total planned 14 doses are based on bodyweight and age group, but total daily dose remains identical for both cohorts regardless of dosing regimen:

- High Dose (Cohort 2: n = 50 [target]):
 - Age group 1: 2.5 mg JNJ-53718678/kg bodyweight
 - Age group 2: 3.0 mg JNJ-53718678/kg bodyweight
 - Age group 3: 4.5 mg JNJ-53718678/kg bodyweight
- Low Dose (Cohort 2: n = 50 [target]):
 - Age group 1: 0.85 mg JNJ-53718678/kg bodyweight
 - Age group 2: 1.0 mg JNJ-53718678/kg bodyweight
 - Age group 3: 1.5 mg JNJ-53718678/kg bodyweight

- Placebo (Cohort 2: n = 50 [target]): those randomized to a placebo regimen will subsequently be randomized 1:1 to receive either:
 - High volume placebo:
 - Age groups 1, 2, and 3: matching placebo (volume of placebo suspension to match the calculated volume of the JNJ-53718678 suspension for the high dose)
 - Low volume placebo:
 - Age groups 1, 2, and 3: matching placebo (volume of placebo suspension to match the calculated volume of the JNJ-53718678 suspension for the low dose)

For analysis purposes, treatment groups will be analyzed and presented regardless of dosing regimen (QD or BID).

1.3. Statistical Hypotheses for Trial Objectives

The primary hypothesis of this study is that JNJ-53718678 has antiviral activity against RSV (i.e. a decrease in RSV viral load area under the curve (AUC) from immediately prior to first dose of study drug [baseline] until Day 5), as assessed by a positive dose-response relationship of JNJ-53718678 compared to placebo.

1.4. Sample Size Justification

The basis of the sample size calculation are the antiviral activity data of Study 53718678RSV1005. In that study, the mean difference in RSV viral load AUC from baseline until Day 5 of the placebo group versus active (adjusted for baseline viral load) was estimated as 105 \log_{10} copies.hour/mL (corresponding to a 25% reduction) and the standard deviation (SD) on the RSV viral load AUC as 85 \log_{10} copies.hour/mL (corresponding to a coefficient of variation [CV] of approximately 20%).

Assuming a more conservative reduction in RSV viral load AUC of 20% compared to placebo, considering a CV of 35% (slightly higher variability than observed in Study 53718678RSV1005), and a 1-sided alpha of 2.5%; the power to conclude a dose-response using the Multiple Comparison Procedure-Modeling (MCP-Mod) procedure under different assumptions for the dose-response relationship (linear, E_{max} and exponential) is provided in [Table 1](#). Based on Study 53718678RSV1005 results, no discrimination between the proposed doses is expected (i.e. E_{max} dose-response shape was observed).

Table 1: Power (%) to Conclude Dose-response Using MCP-Mod Under Different Assumptions for the Dose-response Relationship

Assumed CV	Assumed dose-response relationship		
	Linear	E_{max}	Exponential
Cohort 1 + Cohort 2 (N=74 per treatment arm)			
20%	100.0	100.0	100.0
35%	92.3	95.3	96.6
Cohort 2 only (N=50 per treatment arm)			
20%	99.8	100.0	100.0
35%	79.0	84.0	86.9
Cohort 1 only (N=24 per treatment arm)			
20%	91.5	94.7	96.2
35%	47.1	51.2	54.7

If data of both cohorts are combined (N=74 per treatment arm), the power to conclude dose-response is more than 90% for all 3 different assumptions for the dose-response relationship. If data from Cohort 1 cannot be combined with data from Cohort 2 (e.g. due to inconsistency [means and/or variability] in viral load data between cohorts per treatment group), the power to conclude a dose-response using the MCP-Mod procedure in Cohort 2 (N=50 per treatment arm) is at least 79%.

The sample size in Cohort 1 only ($n \geq 24$ per treatment arm) will provide sufficient power (approximately 90%) if the reduction in RSV viral load AUC is at least 20% with a CV which is not higher than observed in Study 53718678RSV1005 (i.e. 20%).

A sample size of 72 in Cohort 1 and 150 in Cohort 2 is sufficient to detect with reasonable power the antiviral effect; even if the data of Cohort 1 cannot be combined with the data of Cohort 2. Therefore, the primary analysis will be performed after approximately 150 subjects from Cohort 2 have completed the Day 14 assessments (or discontinued earlier). By that time, it is expected that at least 72 subjects from Cohort 1 will have completed the Day 14 assessments (or discontinued earlier).

For Cohort 1, assuming a median time to resolution of symptoms of 3 days in the placebo group, a 1-day reduction in the active group (i.e. ratio of 66%), and a scale parameter of 1/0.65, a sample size of 48 subjects per treatment arm will achieve 95% probability to reach an observed effect in the right direction based on estimates derived from an accelerated failure time model. This will allow an adequate evaluation of clinical course endpoints in the hospital population.

In conclusion, approximately 144 subjects in Cohort 1 (48 subjects per treatment arm) and approximately 150 in Cohort 2 (50 subjects per treatment arm) are planned to be recruited. The sample size of Cohort 2 may be re-estimated to a maximum of 300 in Cohort 2 based upon results from the third IA.

Sample Size Re-estimation

During IA#3 (when approximately 70 to 80 subjects from Cohort 2 have completed the Day 14 assessments [or discontinued earlier]), a sample size re-estimation will be performed to allow an extension of Cohort 2 for the confirmation of the results on selected

clinical course endpoints. Based on all clinical course data from Cohort 2 available at the time of the cut-off for the third IA, one or more clinically relevant endpoint(s) will be selected for confirmation in the final analysis. Time to resolution (i.e. to none or mild symptoms) and reduction in severity of selected clinical signs/symptoms of RSV-related illness are currently expected to be the most relevant clinical endpoints for Phase 3 planning. However, data from this study, in combination with data from other RSV studies within and outside the company, and knowledge obtained through health authority interaction(s) will be considered in IA#3 for the endpoint selection and sample size recalculation for Cohort 2. After selection of (a) clinical endpoint(s), the number of subjects in Cohort 2 will be calculated that is required to minimize the conditional probability of inconclusive results (within the Go-NoGo approach) at the end of the study, assuming a required confidence of 80% (2-sided) to exclude the target value and/or the minimum acceptable value.

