The aforementioned will be presented overall by treatment group and by the subgroups as defined in Section 2.4, for summary parameters, key RSV symptoms and overall RSV symptoms only.

For time to resolution of summary parameters, key RSV symptoms and overall RSV symptoms (ObsRO), sensitivity analyses will be performed considering 4 different imputation methods:

- Method 1: from first resolution (score 0 or 1) after last unresolved value onwards, impute missing data as resolved.

- Method 2: impute all missing values as unresolved (score >1).
- Method 3: impute all missing values in-between resolved observations (score 0 or 1) as resolved.
- Method 4: impute all missing values as unresolved (score >1), except when in-between resolved values where resolved is imputed.

These sensitivity analyses will be provided from IA#3 onwards.

In addition, for the summary parameters, key RSV symptoms and overall RSV symptoms, difference in median time (hours) to resolution (event) between each active treatment group as compared to placebo will be investigated using the AFT model with log-logistic distribution. The model will include class variables treatment group with placebo as reference and randomization stratification factors (derived) and baseline summary parameter score. Summary will include parameter estimates and associated standard error, covariance matrix of parameter estimates, estimated accelerated failure time ratio (as compared to placebo) and both 80% and 95% 2-sided confidence intervals.

The aforementioned will be presented overall by treatment group and by the subgroups as defined in Section 2.4.

Parameter estimates and associated variance matrix resulting from AFT model, will be used in a generalized MCP-Mod approach to test dose-response, at 1-sided alpha level=0.10. The aforementioned MCP-Mod will be presented overall by treatment group only.

Graphical presentation will include:

- Overlay of survival curves with Kaplan-Meier survival function and AFT on one plot
- Forest plot of accelerated failure time ratios and resulting confidence intervals for subgroups of interest as defined in Section 2.4 including the relevant subgroup variable as covariate in the model with subgroup*treatment group interaction.

Status of RSV Symptoms, Status of Health, Status of Improvement of RSV Symptoms, Status of Return to Pre-RSV Disease Health (ObsRO)

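### The 95% behind 48 children per arm in Cohort 1 does not follow from the stated scale of 1/0.65 under the SAP's log-logistic model; the likelier fault is a shape labelled as a scale

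*SAP*

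**What the plan says.** Section 1.4 of the SAP first states that 72 children in Cohort 1, with 150 in Cohort 2, are enough for the antiviral endpoint. It then gives a separate argument for 48 per arm (144 in total) in Cohort 1, based on clinical course:

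- Placebo: "assuming a median time to resolution of symptoms of 3 days in the placebo group".
- Effect: "a 1-day reduction in the active group (i.e. ratio of 66"%).
- Spread, size and result: "a scale parameter of 1/0.65, a sample size of 48 subjects per treatment arm will achieve 95% probability to reach an observed effect".
- Criterion: the estimate need only point the right way; no alpha is attached.
- Model: "based on estimates derived from an accelerated failure time model".

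The section concludes that clinical course in hospitalized children can then be adequately evaluated. It names no AFT distribution, mentions no censoring, and does not say whether the comparison is each dose or pooled active against placebo.

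Elsewhere the SAP does name the distribution for this type of endpoint. In section 5.3.2.2 the difference between each active group and "placebo will be investigated using the AFT model with log-logistic distribution". Section 5.6 uses the log-logistic again for time to resolution of key RSV symptoms in the interim decision rules, comparing high dose with placebo.

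**The concern.** The sentence gives enough inputs to be recomputed, and under the SAP's own model they do not lead to 95%. A scale of 1/0.65 = 1.54 on the log-time axis is a very wide distribution, and the assumed log ratio is then less than one standard error at 48 per arm.

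It matters because this is the only reason the SAP gives for 144 rather than 72 children in Cohort 1. The amendment history says that the rationale and calculations for the increase were placed in section 1.4, yet a reader who checks them cannot confirm them. Either the parameter or the probability is misstated, and the two possibilities have different consequences: one is a wrong label, the other removes the numerical support for the claim of adequacy.

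**Working it through.** **Inputs.** From section 1.4: ratio 2/3 (printed as 66%), scale 1/0.65 = 1.538, 48 per arm, and a criterion with no alpha, namely that the estimated log time ratio is below zero. From sections 5.3.2.2 and 5.6: log-logistic distribution. Assumed, because not stated: each dose against placebo (48 versus 48) and no censoring; both are varied below.

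**Formula.** With scale s, the standard error of the log time ratio is

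- log-logistic: SE = s × √[3(1/n₁ + 1/n₂)], since the information per subject for a logistic location is 1/(3s²);
- Weibull or log-normal: SE = s × √(1/n₁ + 1/n₂).

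The probability of the right direction is P = Φ(|log ratio| / SE), with |log(2/3)| = 0.405.

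**Attempt to reproduce the 95%, log-logistic, 48 versus 48.**

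- Scale 1/0.65 as written: SE = 1.538 × √(6/48) = 0.544; 0.405/0.544 = 0.745; P = 77.2%.
- Scale 0.65: SE = 0.65 × √(6/48) = 0.230; 0.405/0.230 = 1.764; P = 96.1%.

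Size needed for 95%: n = 6s²(1.645/0.405)², about 234 per arm with scale 1/0.65 and about 42 per arm with scale 0.65.

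**Other readings** (the range runs from ratio 2/3 to ratio 0.66):

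| Model and scale | 48 vs 48 | 48 vs 96 (active pooled) |
|---|---|---|
| Log-logistic, 1/0.65 | 77.2–77.8% | 80.5–81.1% |
| Weibull or log-normal, 1/0.65 | 90.2–90.7% | 93.2–93.7% |
| Log-logistic, 0.65 | 96.1–96.5% | 97.9–98.2% |

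**Simulation.** Maximum-likelihood fits (1,500 simulated trials per scenario, ratio 2/3, 48 versus 48, log-logistic) gave 76.7% without censoring and 77.6% with censoring at 21 days for scale 1/0.65, and 97.1% and 96.7% for scale 0.65. Censoring does not explain the gap.

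**Plausibility of the two scales.** With a median of 3 days, the log-logistic quartiles are 3 × 3^(−s) and 3 × 3^(s), and the fraction unresolved at day 21 is 1/[1 + (21/3)^(1/s)].

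- s = 1/0.65: quartiles 0.55 and 16.3 days; 22% of placebo children unresolved at day 21.
- s = 0.65: quartiles 1.5 and 6.1 days; 5% unresolved.

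The caregiver diary is scheduled to end at Day 21 (SAP section 2.1.4, Table 4). The second set fits that schedule more naturally as well as the stated probability.

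**The case against.** The strongest reply is that the 95% may be essentially right. In the log-logistic model the shape is the reciprocal of the AFT scale, so a value written as 1/0.65 looks like a shape given the wrong name. On that reading the result is 96%, about 42 per arm would already reach 95%, and nothing but a word needs changing. This stands, and it is the likelier explanation.

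Second, section 1.4 does not name the log-logistic, and it speaks of the active group in the singular although there are two active arms. The 77% therefore rests on an inference from later sections. This also stands. A Weibull or log-normal model with pooled active arms gives 93–94% at the literal scale, close to the stated figure. If the criterion meant that at least one of the two doses points the right way, those models would give about 97% (two estimates sharing a placebo arm, correlation 0.5). So one cannot say that no common AFT model comes near 95% with scale 1/0.65. However, each of these readings needs a distribution other than the one the SAP specifies for this endpoint and a comparison that section 1.4 does not state.

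Third, the figure feeds nothing later. The sample size re-estimation uses Cohort 2 only, the interim conditional power uses observed estimates, and section 1.2 records Cohort 1 enrolment as complete. This stands, and it limits the point to correcting the record.

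A reader might also infer that Cohort 1 was too small by its own criterion, or that the wrong scale will be carried into Phase 3 planning. The SAP supports neither. The first holds only if the log-logistic scale truly is 1/0.65, and section 1.4 says that endpoint selection and recalculation will draw on data from this and other studies.

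**Conclusion.** The sentence is not reproducible as written. Under the SAP's log-logistic AFT model, each dose against placebo at 48 versus 48 and ratio 2/3, a scale of 1/0.65 gives about 77% (about 81% pooled) instead of 95%. Weibull or log-normal models with that scale give about 90% (93–94% pooled). The stated probability is recovered, at about 96%, when the scale is 0.65.

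The likelier fault is thus a mislabelled parameter, and 48 per arm then stands. The document does not settle this. The 77% depends on taking the log-logistic from sections 5.3.2.2 and 5.6 and on an unpooled comparison; the conclusion that the stated scale and the stated 95% do not fit together under the log-logistic model holds with or without pooling.

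**What to change.** Rewrite the one sentence in section 1.4 so that it names the AFT distribution, states the comparison (each dose, or pooled active, against placebo), and carries consistent figures. For a log-logistic model with each dose against placebo, use one of the following:

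- If the calculation used 0.65: give the scale as 0.65 (shape 1/0.65) and the probability as about 96%.
- If the log-logistic scale really is 1/0.65: give the probability as about 77%. The sentence then no longer supports, on its own criterion, the claim that clinical course can be adequately evaluated, and that claim should be reworded.

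The cost is one sentence and, in the second case, a less favourable stated figure. No change of sample size or planned analysis is asked.

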5.2.3.2. Methods to Control the Type I Error for Multiplicity and Adaptations

Due to the adaptive design, and multiple populations (i.e. full ITT-i analysis set and sub-population based on ITT-i subjects with symptom onset [≤ 3 days relative to randomization]), the Type I error will be controlled using the inverse-normal p-value-combination test as a secondary analysis approach. The total study alpha will be used at the timepoint for the primary analyses which are:

[figure not shown]
- Interim analysis 4 for antiviral effects ($\alpha=5\%$, i.e. 2.5% 1-sided)
- Final analysis for clinical course endpoints ($\alpha=20\%$, i.e. 10% 1-sided)

In a sequential testing framework, this corresponds to the following cumulative α -spending on primary and secondary endpoints:

	IA#1	IA#2	IA# 3	IA#4	Final Analysis
Viral load	0%	0%	0%	5%	5%
Clinical course	0%	0%	0%	0%	20%

This testing procedure will be applied on the ITT-i set

The primary endpoint on viral load ($AUC_{Day\ 5}$) will be tested at alpha of 5% (i.e. 2.5% 1-sided). To account for multiplicity in the statistical evaluation of the key clinical course secondary endpoints, a Bonferroni-Holm procedure will be applied to control for the overall Type I error rate. Clinical course endpoints are tested using an MCP-Mod test at 1-sided alpha level of 10%. Testing of the key clinical course endpoints (time to resolution of key RSV symptoms [ObsRO], incidence of RSV-related complications and change from baseline in key RSV symptoms [ObsRO]) will therefore be started at the 20/3 (6.667)% level. Levels used for testing will be adjusted, in case at least one of the key clinical course endpoints succeeds. The testing strategy is graphically summarized as:

The family wise error rate is strictly controlled at a level below 20% using the considered Bonferroni-Holm procedure.

The study design allows for enrichment at interim analyses 2, 3 and 4. The sample size re-estimation for clinical course endpoints will be conducted at interim analysis 3 only. To control for the multiple potential adaptations (enrichment and sample size re-estimation), the following procedures will be applied. All computations are to be conducted using stage-wise **1-sided** p-values. The final test decision is based on 2-sided p-values. Given the final 1-sided p-value, the 2-sided p-value results as:

- $p_{2\text{-sided}} = 2 \times \min\{p_{\text{reported}}, 1 - p_{\text{reported}}\}$

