Let the cumulative sample sizes for Cohort i up to analysis j be defined as n_{ij} :

	IA#1	IA#2	IA#3	IA#4	Final Analysis
Cohort 1 (n=144)	n_{11} (~36)	n_{12} (~75)	n_{13} (~144)	n_{14} (~144)	n_{15} (~144)
Cohort 2 (n=150)		n_{22} (~36)	n_{23} (~75)	n_{24} (~150)	n_{25} (~300)

RSV RNA Viral Load:

The total sample size planned for the primary analysis on viral load is given as: $n_{\text{Primary}}=294$. This constitutes the sample size of both Cohorts 1 and 2.

Stagewise weights and 1-sided p-values are defined as:

	IA#2	IA#3	IA#4
No enrichment:			
Weight	1		
p-value	p_{14}^F		
Final p-value (global)	p_{14}^F		
Final p-value (sub)	p_{14}^S		
Enrich at IA#2:			
Weight (w_{ij})	$(n_{12}+n_{22})/n_{\text{Primary}}$	$(n_{\text{Primary}} - n_{12} - n_{22})/n_{\text{Primary}}$	
p-value	p_{12}^F	p_{34}^S	
Final p-value (global)	$1 - \Phi \left(\sqrt{w_{12}} \Phi^{-1}(1 - p_{12}^F) + \sqrt{w_{34}} \Phi^{-1}(1 - p_{34}^S) \right)$		

	IA#2	IA#3	IA#4
Final p-value (sub)	$1 - \Phi \left(\sqrt{w_{12}} \Phi^{-1}(1 - p_{12}^S) + \sqrt{w_{34}} \Phi^{-1}(1 - p_{34}^S) \right)$		
Enrich at IA#3:			
Weight (w_{ij})	$(n_{13}+n_{23})/n_{Primary}$	$(n_{Primary}-n_{13}-n_{23})/n_{Primary}$	
p-value	p_{13}^F	p_{44}^S	
Final p-value (global)		$1 - \Phi \left(\sqrt{w_{13}} \Phi^{-1}(1 - p_{13}^F) + \sqrt{w_{44}} \Phi^{-1}(1 - p_{44}^S) \right)$	
Final p-value (sub)		$1 - \Phi \left(\sqrt{w_{13}} \Phi^{-1}(1 - p_{13}^S) + \sqrt{w_{44}} \Phi^{-1}(1 - p_{44}^S) \right)$	

- p_{ij}^F defines the p-value for the MCP-Mod test for data collected from in stages i to j in the full population
- p_{ij}^S defines the p-value for the MCP-Mod test for data collected from in stages i to j in the sub population

A p-value combination for the test of the sub-population is required, as the enrichment decision implies a sample size re-calculation for the sub-population.

Clinical Course Endpoints:

Sample size for clinical course endpoints is only based on Cohort 2. Let $n_{Primary} = 225$ be defined as midway between planned ($N= 150$) and maximum sample size ($N=300$).

	IA#2	IA#3	IA#4	Final Analysis
No enrichment:				
Weight (w_{ij})	$(n_{23})/n_{Primary}$		$(n_{Primary}-n_{23})/n_{Primary}$	
p-value	p_{23}^F		p_{45}^F	
Final p-value (global)	$1 - \Phi \left(\sqrt{w_{23}} \Phi^{-1}(1 - p_{23}^F) + \sqrt{w_{45}} \Phi^{-1}(1 - p_{45}^F) \right)$			

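### Section 1.4 lets the endpoints for final confirmation be chosen on IA#3 data, while the error control claimed in Section 5.2.3.2 holds only if all three named endpoints are always tested by Holm

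*SAP*

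**What the plan says.** SAP Section 1.4, under Sample Size Re-estimation, describes a choice made at IA#3, when about 70 to 80 outpatients have reached Day 14. The choice is made "Based on all clinical course data from Cohort 2 available at the time of the cut-off for the third IA", and as a result "one or more clinically relevant endpoint(s) will be selected for confirmation in the final analysis". The list of candidates is open: two kinds of endpoint are named as currently the most likely, but results from other RSV studies and health authority advice "will be considered in IA#3 for the endpoint selection and sample size recalculation for Cohort 2".

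Section 5.2.3.2 describes the final test. "Clinical course endpoints are tested using an MCP-Mod test at 1-sided alpha level of 10" per cent. The family is fixed at three: time to resolution of key RSV symptoms, incidence of RSV-related complications, and change from baseline in key RSV symptoms. Testing "will therefore be started at the 20/3 (6.667)% level" (two-sided). The section then states: "The family wise error rate is strictly controlled at a level below 20% using the considered Bonferroni-Holm procedure". The final p-value combines p23 (Cohort 2 data up to IA#3) with p45 (data after it), with weights built on n_Primary = 225. On what the combination test is meant to cover, it says: "To control for the multiple potential adaptations (enrichment and sample size re-estimation), the following procedures will be applied".

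Section 5.6 uses the same three endpoints at the interim analyses. It sizes the Cohort 2 extension to limit an inconclusive result to 20% on all clinical endpoints and mentions no selection.

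**The concern.** The two sections give different rules for what is tested at the end. Section 1.4 has a family chosen after looking at the data. Section 5.2.3.2 has a fixed family of three. The SAP never says how a selected endpoint enters the Holm family, so two statisticians could run different final tests from the same document.

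The difference matters because the children whose data inform the choice stay in the test through p23. Inverse-normal weighting protects against data-driven changes to the second stage. It does not make the first-stage p-value of the best-looking endpoint valid; that needs multiplicity correction over every candidate. Endpoint selection is also absent from the adaptations that the section says it covers. An endpoint picked because it looked best, and then tested with those data at a level that ignores the choice, is favoured towards success, and its estimated effect is too large. The clinical results are meant to inform Phase 3 planning.

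**Working it through.** **Inputs from the SAP.** Clinical alpha 10% one-sided, 20% two-sided (5.2.3.2). Three named endpoints. Cohort 2 size at IA#3 n23 of about 75. n_Primary = 225. Hence w23 = 75/225 = 1/3 and w45 = 2/3, and the final statistic is Z = √(1/3)·Z1 + √(2/3)·Z2.

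**Assumptions, not in the SAP.** Each endpoint's stage result is treated as one normal statistic. The correlation between endpoints is equal for all pairs and is varied from 0 to 0.8. Selection takes the largest Z1. There is no true effect on any endpoint. Candidate numbers above three are illustrative. Each simulated figure rests on 400,000 runs.

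**The plan's own figures.** 20%/3 = 6.667% two-sided, or 10%/3 = 3.333% one-sided. For three independent endpoints, 1 − (1 − 0.06667)³ = 18.7% two-sided and 1 − (1 − 0.03333)³ = 9.7% one-sided. The stated level and bound reproduce for a fixed family.

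**One-sided error against 10%, SAP weights:**

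| Final test | corr. 0 | corr. 0.5 | corr. 0.8 |
|---|---|---|---|
| All three, Holm over three | 9.7% | 8.1% | 6.4% |
| Best 1 of 3, kept at one third of alpha | 7.3% | 6.1% | 5.1% |
| Best 2 of 3, Holm over two | 13.4% | 11.1% | 8.9% |
| Best 1 of 3, full alpha | 19.4% | 16.5% | 14.1% |
| Best 1 of 8, full alpha (8 assumed) | 30.2% | 22.9% | 17.5% |
| Best 3 of 8, Holm over three (8 assumed) | 20.5% | 14.0% | 9.2% |

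**Two-sided error against 20%.** Holm over all three gives 18.7%, 16.3% and 12.8%. Best 1 of 3 at full alpha gives 22.1%, 21.0% and 20.4%. The two-sided excess is small because choosing the most favourable result makes a rejection in the unfavourable direction less likely. The excess lies on the favourable side.

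**Sensitivity to the timing of IA#3.** With 70 or 80 children instead of 75, best 1 of 3 at full alpha and correlation 0.5 gives 16.3% or 16.9%.

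**Bias.** With three candidates and correlation 0.5, the selected endpoint's Z1 averages about +0.60 when nothing works. Its contribution to the final statistic is √(1/3) × 0.60 = 0.35.

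**Selected endpoint tested on later data only.** One selected endpoint, tested in place of the three on p45 alone, has one-sided error of 10.0%. Tested in addition to Holm over three, with no alpha share, the independent case gives 1 − (1 − 0.0967)(1 − 0.10) = 18.7%. Simulation over the same correlations gives about 13% to 19%. Later data remove the selection bias but not the extra multiplicity.

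**The case against.** The strongest reply is that the operative test contains no selection step. Sections 2.3.2, 3, 5.2.3.2 and 5.6 all list the same three clinical endpoints. No section drops one from the Holm family, adds one, or assigns a selected endpoint the full 10%. With Holm over all three, looking at the IA#3 results first costs nothing. The Section 1.4 sentence stands under sample size re-estimation, and what follows it is a sample size calculation in the Go/No-Go framework, so it can be read as choosing the endpoint that drives the sample size. Section 3 limits the efficacy results shown to the IDMC to viral load and the three key endpoints, although it allows the IA#3 and IA#4 analyses to be extended.

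This stands as far as it goes. The error statement is true of the family it describes. It does not remove the conflict, because Section 1.4 speaks of selection for confirmation in the final analysis, not only for sizing.

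It is also fair that selection by largest Z is a worst case, since clinical relevance and outside evidence enter the choice, and that Section 5.1.1 calls the study exploratory and the error-controlled procedure a secondary approach.

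A reader might go further and infer that the final clinical test is inflated whatever is done. The SAP does not support that: the inflation depends on a reading of Section 1.4 that Section 5.2.3.2 does not implement. Nor does it support larger error rates based on a weight of 75/150, because the combination test for clinical endpoints fixes the denominator at 225.

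**Conclusion.** The point holds as a contradiction with a conditional cost. Section 1.4 permits a route on which the control claimed in Section 5.2.3.2 is lost. If one of the three endpoints is selected and tested alone at full alpha with the SAP weights, one-sided error is about 14% to 19% against 10%, and two-sided error 20.4% to 22.1% against 20%, for correlations of 0.8 down to 0. A longer candidate list makes it worse, but its length is not given, so figures for it are illustrative. If all three endpoints are always tested at their Holm levels, error stays within both limits whatever IA#3 shows.

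A reader might infer that the main result of the trial is at risk. It is not: the primary viral load test does not depend on this choice. The affected analysis is secondary, in an exploratory study. The change should be made because the document claims strict control and only wording stands in the way of having it.

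**What to change.** Reword the Section 1.4 sentence so that selection at IA#3 decides only which of the three key endpoints drives the Cohort 2 sample size. State there that the final family remains the three endpoints of Section 5.2.3.2, with Holm over all three, whatever IA#3 shows. Align the sizing criterion with Section 5.6, which currently refers to all clinical endpoints.

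Any other endpoint chosen at IA#3 should be reported as exploratory, outside the error-controlled family, using children enrolled after IA#3 (stage p45) so that its estimate is free of selection bias. If the sponsor wants to test it formally, give it an explicit share of alpha before IA#3 and reduce the share of the three accordingly.

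The cost is SAP wording. The sponsor gives up the freedom to put all clinical alpha on one endpoint after IA#3, and a newly chosen endpoint is estimated without the first 75 or so outpatients.
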